1. BACKGROUND AND RATIONALE

1.1. General Introduction

Free gingival graft (FGG) procedure is commonly conducted to increase the width of keratinized gingiva around teeth and implants. Although FGG procedure has predictable clinical outcomes, morbidities and complications on the donor sites (palate) usually affect patients' willingness to receive the procedure (Griffin et al. 2006). Several alternative materials, such as allogenic dermal matrix or xenogeneic collagen matrix, have been used to prevent these complications, but these substitutes have inferior clinical results to FGG (McGuire and Scheyer 2014; Wei et al. 2000). Since FGG has an irreplaceable position in augmenting keratinized gingiva, clinicians utilize dressings to improve palatal wound healing (Shanmugam et al. 2010; Thoma et al. 2016). Allogenic amnion chorion membrane (ACM) has been used to facilitate wound healing, such as diabetic ulcer (Zelen et al. 2013), chronic wounds (Forbes and Fetterolf 2012) and perforated sinus membrane (Holtzclaw 2015) because this placental membrane retains extracellular matrix proteins, growth factors and cytokines to promote cell proliferation and control inflammation at the wound (Koob et al. 2013). Additionally, allogenic amnion chorion membrane can be well attached to the wound because of its thin thickness and flexibility. Due to these characteristics, allogenic amnion chorion membrane might be an excellent dressing for palatal wound after harvesting a FGG.

1.2. Rationale and justification for the Study

a. Rationale for the Study Purpose

So far, there is no strong evidence supporting the clinical impact of any dressings or membranes on the healing of the FGG donor site. It is very important to assess the effects of the allogenic amnion chorion membrane on the wound of the FGG donor site given this membrane has the potential to improve wound healing and reduce complications.

b. Rationale for Materials Selected

The ACM (allogenic amnion chorion membrane, BioXclude®, SNOASIS MEDICAL) is a commercial product and has multiple sizes available. It has been used for tissue healing and tissue regeneration in dentistry. Based on the available evidence, it has the potential to improve wound healing of the FGG donor site. The collagen dressing, CLD (Collagen Patch®, Zimmer), is a common product used for tissue healing in dentistry (Shanmugam et al. 2010). It is selected as a dressing material to cover the wound in the control group.

c. Rationale for Study Population

The study will recruit subjects who need free gingival graft surgery. The dressings, ACM or CLD, will be placed in the wound of the FGG donor site. These subjects

should be systemically healthy and are able to receive FGG surgery.

d. Rationale for Study Design

It is a randomized controlled and split-mouth design study. The randomized controlled trial (RCT) is usually considered the gold standard for a clinical trial and it is able to provide the highest level of evidence within all the study designs (Howick et al. 2011). The split-mouth design is a popular design in oral health research. Two treatments (test and control) are randomly assigned to either the right or left halves of the dentition/palate. This design removes a lot of inter-individual variability from the estimates of the treatment effect given two treatments are performed in the same subject (Lesaffre et al. 2009).

2. HYPOTHESIS AND OBJECTIVES

2.1. Hypothesis

Null hypothesis:

Healing at the palatal wound covered with an allogenic amnion chorion membrane and the collagen dressing has no significant difference. Alternative hypothesis:

The palatal wound covered with an allogenic amnion chorion membrane heals faster than the palatal wound covered with a collagen dressing. The patients with an allogenic amnion chorion membrane feel less pain and have fewer complications than the patients with a collagen dressing.

2.2. Primary Objectives

This study aims to compare an allogenic amnion chorion membrane (BioXclude®, SNOASIS MEDICAL) to a collagen dressing (Collagen Patch®, Zimmer) in the palatal wound healing from the clinical and histological perspectives.

2.3. Secondary Objectives

In addition to the outcomes of wound healing, the clinician's feedback with these two materials (ACM and CLD), such as handling and operation time, will also be evaluated.

2.4. Potential Risks and Benefits:

a. End Points - Efficacy

All eligible patients need FGG procedure and will receive the appropriate treatments. The patients may have improved healing or may not have additional clinical benefits by participating in this clinical study.

b. End Points - Safety

1) Study related risks:

Initial infection, pain, swelling, and bleeding related to FGG procedure and gingival

biopsy; adverse outcomes of the receipt sites; The patients will have the same risks if they receive the same treatment without participating in the study.

2) Protection against risks:

All efforts will be made to minimize risks to all and every participant: only patients with the need for FGG procedure will qualify for the study.

3. STUDY POPULATION

3.1. List the number of subjects to be enrolled.

The proposed project is a pilot study. We use a convenient sample size based on the budget. We will recruit 19 patients in total, and with a dropout rate of 15%, we will have a sample size of 15.

With 15 patients, we can detect an effect size as small as 0.7 between two treatments for the two main outcomes (the area of healing and VAS pain score at week 2), by a paired t test assuming a within-subject correlation of 0.6 at the significance level of 0.05 with 80% power.

3.2. Criteria for Recruitment

The patients who need FGG procedure will be recruited in the study. These patients should be systemically healthy to receive this procedure.

3.3. Inclusion Criteria

Nineteen subjects will be recruited among the patients attending the Clinic for Graduate Periodontics, UTSD, who are in need of a FGG procedure to augment keratinized gingiva, augment ridge or cover recession defects. The size of the FGG that the patient needs will not be bigger the size of FGGs that have to be harvested in this study (two 8mm (width) x 10mm (length) x \approx 1.5mm (thickness) FGG). All subjects are \geq 18 year-old and systemically healthy or with controlled common systemic conditions, such as hypertension, that will not affect wound healing.

3.4. Exclusion Criteria

Patients will be excluded if they are current heavy smokers(>10 cigarettes/day), have diabetes or other systemic diseases that may comprise healing, take antibiotics and/or analgesics within one week before the procedure and have loss of sensation on the palate. Patients who stop smoking more than one year are eligible.

3.5. Withdrawal Criteria

A subject may be discontinued from participation in the study for any of the following reasons:

1. Withdrawal of consent
2. Subject noncompliance with the protocol, as determined by the investigator
3. Any event or condition that would make continued participation in the study not in the best interest of the subject, as determined by the investigator
4. Pregnancy
5. Development of any medical condition that might affect the treatment and clinical outcomes, as determined by the investigator.
6. Initiation of any treatment or exposure that might affect the healing outcomes of the FGG donor site, as determined by the investigator.

7. Investigator discretion

3.6. Subject Replacement

Subjects who withdraw from the study can be replaced. However, to complete the study within the time allocated, the center will not enroll subjects after 24 months from enrollment initiation.

4. TRIAL SCHEDULE

There will be eight appointments including the baseline appointment and seven follow-up appointments (4 days, 10 days, 2, 3, 4, 6, 8 weeks) after the surgery. The details of each visit will be mentioned in 6.3. Study Visits and Procedures.

5. STUDY DESIGN

5.1. Summary of Study Design

This randomized controlled and split-mouth design study aims to compare an allogenic amnion chorion membrane (BioXclude®, SNOASIS MEDICAL) to a collagen dressing (Collagen Patch®, Zimmer) in the palatal wound healing from the clinical and histological perspectives. Nineteen patients will be recruited. The wound healing would be assessed using pictures and questionnaires at multiple time points. A biopsy will be done to evaluate histological healing. Patients will not have additional complications other than the complications from FGG procedure. However, the size of wounds will be larger than the size required to treat defects. The hypothesis is that the patients with an allogenic amnion chorion membrane feel less pain and have fewer complications than the patients with a collagen matrix. The potential application of the allogenic amnion chorion membrane in palatal wound will benefit patients who receive FGG procedure. The results can be applied in managing various wounds in the oral cavity in the future.

6. METHODS AND ASSESSMENTS

6.1. Randomization and Blinding

Site allocation (right or left side of the palate) to the two groups (ACM or CLD) will be performed by the investigators before the surgeon harvests FGGs, based on computer-generated randomization (R Statistical Software). Patients will be blinded because they will not know which dressing is in the test group or the control group.

6.2. Contraception and Pregnancy Testing

Pregnancy status of subjects who are women with childbearing potential will be orally confirmed at the screening. The pregnant subjects will be excluded from the study.

6.3. Study Visits and Procedures

a. Screening Visits and Procedures

Study protocol and consent forms will be approved by the Institutional Review Board at the University of Texas Health Science Center at Houston. The trial will be registered with ClinicalTrials.gov. The clinicians in UTSD will be told the information of this clinical trial. The potential subjects will be identified in the clinic of Department of Periodontics, for initial screening. The principal investigator will confirm the eligibility of these patients.

All patients will sign the consent forms and are informed of the details of study procedures as well as potential complications. After informed consent is obtained, the surgery will be scheduled as the first visit. An impression will be taken to make the stent before the surgery.

b. Study Visits and Procedures

Patients will have FGGs harvested from two sites on the palate (right and left; the area between canine to first molar). In addition to the FGG wounds, two palatal gingiva biopsies will be harvested. The size of the FGG will be standardized (8mm (width) x 10mm (length) x \approx 1.5mm thickness). FGGs will be harvested by the #15 blade with the assistance of a template stent. Two FGGs will be used based on the patient's need. If the patients need grafts larger than two standardized FGGs in one procedure, the patients will be excluded from the study. The biopsies of palatal gingiva will be harvested by a tissue punch and the size is standardized (4mm (diameter) x \approx 1.5mm thickness). The area of biopsy will be at least 3mm away from the FGG wound. Biopsies and FGGs will be harvested in the area between maxillary canine and first molar where tissue grafts are commonly harvested from (Reiser et al. 1996). These wounds can be completely healed even without placing any dressing materials (Harris et al. 2007). Dressing materials are used to improve healing and reduce complications. The wounds of FGG and biopsy will be covered with an allogenic amnion chorion membrane (ACM, BioXclude®) or a collagen dressing (CLD, Collagen Patch®) based on the randomization table.

Clinical Measurements

The donor sites of FGG will be evaluated on 4 days, 10 days, 2 weeks, 3 weeks, 4 weeks, 6 weeks, 8 weeks after the surgery (7 follow-up visits in total). Healing of the donor site will be analyzed based on (1) the degree of epithelialization, (2) the size of wound area, (3) color match and (4) bleeding condition.

(1) Epithelialization will be evaluated at each follow-up visit until the wound is completely epithelialized. It is measured by means of bubble formation after dripping hydrogen peroxide (3%) to the wound surface and epithelialization will be ranked as total, partial or none (Keceli et al. 2015; Marucha et al. 1998);

(2) The wound area will be assessed by means of a clinical picture taken at each follow-up visit (Del Pizzo et al. 2002; Thoma et al. 2012). The picture will be taken with an angulation perpendicular to the wound. A periodontal probe will be placed by the wound as a reference scale. Wound area is defined as the area without

epithelization. The wound area on the picture will be measured by ImageJ; (3) Color match of the donor site will be identified at every visit by using a 4-point scale: 1. Obvious difference; 2. Noticeable difference; 3. Disguisable difference; 4 No noticeable difference in comparison with adjacent gingiva. Three measurements, (1), (2), and (3), will be performed by one independent examiner who does not know the dressing (ACM or CLD) for each wound; (4) Haemostasis has to be achieved when no bleeding is actively seen. Delayed bleeding, prolonged haemorrhaging from the palate during the postsurgical period, reported by the patient, will be documented (Del Pizzo et al. 2002).

The wound healing will also be evaluated from the patient's perspective by means of (5) pain and (6) sensibility. Patients will be given a questionnaire to answer these questions every day or at the scheduled appointments (4 days, 10 days, 2 weeks, 3 weeks, 4 weeks, 6 weeks, 8 weeks) until the patient completes the study.

(5) Pain will be assessed by using VAS pain scores (0 to 10. 0: no pain, 1: minimal pain, 10: severe pain) (Keceli et al. 2015);

(6) Sensitivity will be assessed by means of a periodontal probe (XP 23/UNC 15, Hu-Friedy) using a 4-point discrimination scale (coronal, apical, mesial, distal) around the donor area, before the surgery and at the follow-up visits. Sensibility will be recorded using a rubbing movement and a pin-pressure nociception. Patients will be asked to give a rating of their loss of sensibility based on a three-point verbal descriptor scale (VDS): none, mild or moderate, severe) (Del Pizzo et al. 2002);

(7) The surgeons will be given a questionnaire to answer questions regarding handling of the two different materials after performing the surgery.

Volumetric Analysis

The impression of FGG donor site will be obtained using intraoral scanner at pre and post-operatively 4 days, 10 days, 2 weeks, 3 weeks, 4 weeks, 6 weeks, 8 weeks. The STL files of pre-op and post-op will be imported into the reverse engineering software. Then, three-dimensional images will be reconstructed and superimposed to allow for the measurement of volumetric change within the initial harvested area during wound healing phase. 10% of the sites will be randomly selected for repeated measurements.

Histological and Histomorphometric Analyses

Gingival specimens (4mm in diameter, 1.5mm in thickness) will be harvested at baseline visit and the 10-day follow-up visit for histological and histomorphometric analyses. The second biopsy will be performed at the 10-day follow-up visit because epithelization will not be completed before two weeks. The tenth day is a proper timing to evaluate early healing. Specimens will be cut in sections (5 μ m in thickness) and stained with either H&E to identify the cellular composition of inflammatory infiltrates or Masson's trichrome to detect new collagen depositions. For qualitative histological analysis, the histological sections will be evaluated using a Nikon light microscope, using Nikon NIS Element AR Imagine Software (Nikon Metrology, Inc. Brighton, MI) to calculate the percentages of the new collagen and matured collagen, as well as the thickness of the epithelium automatically. Three regions of interest will be analyzed on each specimen corresponding to the superficial, central, and apical third. Immunohistochemical staining will be performed to detect factor VIII (von Willebrandt factor) to detect endothelial cells and therefore angiogenesis. The area of angiogenesis will be quantified using the same Nikon NIS Element AR Imagine Software.

c. Final Study Visit:

The 8-week follow-up will be the subject's last visit for this clinical trial. The patients will have clinical measurements as previously mentioned and received the gift card.

d. Post Study Follow up and Procedures

The subjects will continue having routine maintenance appointments to follow up the outcomes related to the surgery and periodontal health in the periodontics clinic of UTSD. If the patients have symptoms or complications, the necessary treatments, will be performed.

e. Discontinuation Visit and Procedures

Subjects are free to withdraw from participation in the study at any time upon request. A subject may be discontinued from participation in the study for any of the following reasons:

1. Withdrawal of consent
2. Subject noncompliance with the protocol, as determined by the investigator
3. Any event or condition that would make continued participation in the study not in the best interest of the subject, as determined by the investigator
4. Pregnancy
5. Development of any medical condition that might affect the treatment and clinical outcomes, as determined by the investigator.
6. Initiation of any treatment or exposure that might affect the outcomes of implant therapy, as determined by the investigator.
7. Investigator discretion

Any subject with a serious adverse event, such as life-threatening diseases, hospitalization, that is ongoing at the time of discontinuation will be followed until the event returns to baseline, resolves, or stabilizes. If the serious adverse event does not meet these outcomes within 30 days after discontinuation or after study completion, the subject will be referred to an appropriate practitioner for continued care. If the study is discontinued, subjects will be referred back to the qualified clinicians for necessary dental care.

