7. TRIAL MATERIALS

7.1. Trial Product (s)

Allogenic amnion chorion membrane (ACM), BioXclude, is a minimally manipulated allograft amnion chorion tissue for use as a wound covering in dental surgery. It has been widely used in dentistry. Its unique physical and biological properties provide the benefits of a growth factor and an occlusive barrier. The tissue used in BioXclude is obtained from consenting mothers who donate their placentas after elective caesarian section delivery. The amnion chorion tissue is processed using a patented tissue processing technology (Purion®,) designed to cleanse and maintain the delicate structures of the tissue. Following processing and dehydration, the allografts are packaged and terminally sterilized. This processing methodology allows for

retention of the biological factors found in native amnion chorion tissue.

Collagen dressing (Collagen Patch®, Zimmer) is used to cover wound in dental surgery. It can adhere to the wound and retain its structural integrity even when wet. It is known to control bleeding and stabilize blood clots as well as protect the wound bed while accelerating the healing process.

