8.2. Specific Restrictions / Requirements

Patients will be prescribed an analgesic (Ibuprofen, 600 mg, q.i.d; if the patient cannot take ibuprofen, 500mg acetaminophen, q.i.d will be prescribed). A disinfectant solution (Chlorhexidine digluconate, 0.2% solution) will be prescribed but the patient will only apply the solution to the recipient site using a monojet syringe (q 8 hours, 10 days). An individualized protective stent will be given to the patient. The patient will be instructed to wear the stent overnight after the surgery and continue wearing it for 10 days. The patient will be instructed to take liquid diet for the first 2 days then soft diet till the 10th day. Sutures at the FGG site will be removed 4 days after surgery.

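### Examiner masking is stated but not protected: dressing still present at day 4 or day 10 could be read as wound and could reveal the sides before week-2 wound area is measured

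*Combined protocol and SAP*

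**What the plan says.** Section 6.3 has both palatal wounds covered at surgery, one with the amnion chorion membrane (ACM) and one with the collagen dressing (CLD). Sections 4 and 6.3 set follow-up at days 4 and 10 and at weeks 2, 3, 4, 6 and 8.

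The clinical measurements in 6.3 include a peroxide bubble test for epithelialization, a photograph measured in ImageJ for wound area (defined as the part not yet epithelialized), and a four-point colour score. These three "will be performed by one independent examiner who does not know the dressing (ACM or CLD) for each wound". An intraoral scan is taken on the same schedule.

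Section 1.1 describes ACM as thin, flexible and well attached to the wound. Section 7.1 calls it an occlusive barrier and says of CLD: "It can adhere to the wound and retain its structural integrity even when wet". No section says when either product is resorbed or removed, or what is done if some is still present at a visit.

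Sections 3.1 and 11.1 name "the two main outcomes (the area of healing and VAS pain score at week 2". Section 8.3 says that the surgeons are not blinded.

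**The concern.** Masking of the examiner is asserted, and no procedure keeps it. The same person sees each palate at days 4 and 10 and also measures the week-2 photographs. Nothing in 6.3 codes the photographs, separates the tracing from the clinic visits or adds a second reading; the 10% repeat measurement appears only under the volumetric analysis. In a split-mouth design, recognising the product on one side identifies the other.

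Two things would follow if dressing remained at an early visit:

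- The peroxide test, photograph, colour score and scan at that visit could describe the product on the wound instead of the wound.
- The examiner could carry knowledge of the allocation into the week-2 area measurement. That measurement needs judgement: 6.3 itself expects epithelialization to be incomplete before two weeks, so many wounds may still have an edge to place. The study hypothesis is directional ("The palatal wound covered with an allogenic amnion chorion membrane heals faster than the palatal wound covered with a collagen dressing"), so an informed reader may have an expectation.

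**Working it through.** **Step 1. What the text establishes, and what it leaves open.**

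| Question | Documents |
|---|---|
| First assessment | Day 4 (4, 6.3) |
| Are the dressings distinguishable? | Described differently: thin membrane and collagen patch (1.1, 7.1) |
| Do they adhere? | Both described as adhering or attaching (1.1, 7.1) |
| How long do they stay? | Not stated |
| Rule for residual material | None |
| Who grades and measures? | One examiner for all three ratings (6.3) |
| Is tracing separated from chairside viewing? | Not stated |
| Main outcome affected | Area of healing at week 2 (3.1, 11.1), taken here to be the photographic wound area of 6.3 |

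The link to the main outcome therefore has three conditions: material remains at day 4 or day 10, the examiner recognises it, and that knowledge shifts the week-2 measurement. The documents rule out none of them and establish none of them. A day-4 reading of the dressing does not itself change the week-2 value; the only route is unmasking.

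**Step 2. Reproduce the plan's own figure.** Sections 3.1 and 11.1 say "we can detect an effect size as small as 0.7 between two treatments" with 15 patients, "by a paired t test assuming a within-subject correlation of 0.6 at the significance level of 0.05 with 80% power". Reading 0.7 as a difference in units of the single-site SD:

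- SD of the paired difference = √(2(1 − 0.6)) = √0.8 = 0.894 SD
- Standardised paired difference = 0.7 / 0.894 = 0.783
- Noncentrality = 0.783 × √15 = 3.03, with 14 degrees of freedom and a two-sided critical value of 2.145
- Power from the noncentral t distribution = 80.5%; the smallest detectable difference at 80% power is 0.696 SD

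The plan's figure reproduces. The plan does not state sidedness; two-sided 0.05 fits. Nothing in this point changes the sample size.

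**Step 3. Illustrate what unmasking could do to the week-2 test.** The documents give no size for examiner bias, so the shift b below is an assumption. With no true difference, n = 15, correlation 0.6 and two-sided 0.05, a systematic shift of b SD toward one side gives noncentrality (b / 0.894) × √15:

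| Assumed shift b (SD) | Noncentrality | Chance of p < 0.05 |
|---|---|---|
| 0 | 0 | 5.0% |
| 0.1 | 0.43 | 6.9% |
| 0.2 | 0.87 | 12.7% |
| 0.3 | 1.30 | 22.8% |
| 0.5 | 2.17 | 52.2% |

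The table shows how sensitive the test is to a shift. It does not estimate what will happen.

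**The case against.** The strongest reply is that the premise is undocumented. No section gives a residence time, and if both products are gone by day 4 the concern has no effect. That stands, and the point is worded conditionally because of it.

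Several stronger readings are tempting and are not supported:

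- **That the dressings are known to be in place until day 4.** A reader might infer this from 8.2: "Sutures at the FGG site will be removed 4 days after surgery". Elsewhere the palate is called the FGG donor site, so this sentence may mean the recipient site. No section says that the dressings are sutured. The wet-integrity statement for CLD gives no duration.
- **That the day-4 visit shows the examiner the allocation.** The text supports only that it could.
- **That residual dressing would inflate the volume results by a known amount.** A scan used for "measurement of volumetric change within the initial harvested area during wound healing phase" could include residual material, but the documents give no dressing thickness, so any percentage would be the product of a chosen input. Volume is also neither a main outcome nor in the outcome list of 11.2 c.
- **That both main outcomes are at risk.** VAS pain is reported by the patient and is not affected by examiner unmasking.

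It can also be said that this is a budget-sized pilot with exploratory comparisons and a stated masked examiner. That limits the weight of the point. It does not remove the gap, because week-2 area is named as a main outcome and a significance level is set for the primary endpoint. Finally, coded tracing by the same examiner cannot mask the chairside peroxide and colour grades, and it cannot erase memory of a palate. Both limits stand and should be reported.

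**Conclusion.** The concern holds in conditional form. The protocol relies on a masked examiner from day 4 onward, does not state when the dressings are gone, and has no step that keeps the week-2 area measurement apart from what was seen at days 4 and 10. Readings at those visits could partly describe product, and the masking of one of the two main outcomes could be lost.

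The documents do not determine the size. It is zero if no dressing remains at day 4 or if the examiner cannot recognise it. Under assumed shifts of 0.1 to 0.3 SD, the 5% error rate for week-2 area would become 6.9% to 22.8%. The change is worth making because coded, deferred tracing reduces possible bias in that outcome whether or not dressing persists.

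**What to change.** Amend 6.3 as follows.

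(a) The examiner traces all photographs in ImageJ after the last patient visit. The files are coded without patient, side or visit, are cropped or mirrored so that the anatomy does not give the side away, and are presented in random order. Day-4 images, and any others that show dressing, form a separate batch traced last.

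(b) At day 4 and day 10 a clinician other than the masked examiner records on the CRF, for each side, whether dressing remains.

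(c) No site is excluded. Values from sites with residual dressing are flagged, and that visit's comparisons are reported descriptively with and without them and are not interpreted as healing differences. Simply dropping such sites from the analysis would be a post-randomisation exclusion on something the products themselves influence, and in a paired analysis losing one side loses the pair.

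(d) The report states that the chairside peroxide and colour grades may not have been fully masked.

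The cost is file handling, one form field completed by someone already at the visit, and wound-area results that are available only after the last patient visit. No additional reader, visit or patient is needed.
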